## 11 STATISTICAL CONSIDERATIONS

### 11.1 Study design/Endpoints:

#### **Arm A and Arm B**

The primary endpoint of this phase II study is to assess objective response rate of sorafenib (BAY 43-9006) in metastatic medullary thyroid carcinoma in setting of inherited tumor syndromes as well as in setting of sporadic medullary thyroid cancer.

For this Phase II study, we have chosen the minimax two-stage design of Simon resulting in a trial with two stages with decisions to continue after 16 and 25 response-evaluable patients are accrued to each cohort (Arms A and B) (Simon *et al.*, 1989).

This design minimizes the expected sample size given specified alpha and beta error rates. For example, we will define the true minimum response rate,  $p_0$ . This is a response probability, at which or below, we consider the agent to be clinically unimportant, ineffective, or uninteresting. Associated with this probability is the alpha error rate, the probability of failing to reject an agent with a response rate  $\leq p_0$ . On the other hand, we will designate 'upper' target response rate,  $p_1$ , with its associated error rate, beta. The beta error is the probability of falsely rejecting an agent with a response rate of  $\geq p_1$ . Using exact binomial probabilities, the Simon design generates two study sample sizes. At the first stage, if  $r_1$  or fewer responses are observed in  $n_1$  patients, the study is terminated. If the number of observed responses is greater than  $r_1$ , the study is continued to the maximum sample size,  $n$ . If in  $n$  patients,  $r$  or fewer responses are observed, the agent is considered ineffective and no further study is warranted. For the given  $p_0$ , one can calculate the expected sample size, EN ( $p_0$ ), and the probability of early termination, PET ( $p_0$ ).

We will consider sorafenib (BAY 43-9006) to be ineffective or uninteresting if the true response [PR+CR using unidimensional RECIST/WHO response criteria] probability is less than 10% ( $p_0$ ). We will also assume that the regimen is worthy of further study if the true response probability or target response rate is 30% or greater ( $p_1$ ). These figures result in a two-stage design of 16 and 25 patients, with an alpha of 0.10 and beta of 0.10. If one or no responses are seen in the first 16 response-evaluable patients, the study is terminated early and this regimen is deemed ineffective for this patient population. If two or more patients respond in the first 16, an additional 9 patients are treated for a total of 25. If 5 or more patients respond of the 25, we will recommend that the regimen be studied further. If 25 patients are treated, we will be able to estimate the frequency of response with a 95% confidence interval of not greater than 19.6%.

Similarly, the 25 patients in each of Arms A and B will allow us to estimate the probability of a specific toxicity to within  $\pm 19.6\%$  in each cohort. Any toxicity occurring with at least a 10% probability has a 92.8% chance of being seen at least once in 25 toxicity-evaluable patients.

### **11.2 Sample Size/Accrual Rate:**

For this study of 16 or 25 patients in Arm A and 16 or 25 patients in Arm B, we estimate that we will accrue 3-4 patients per month, and meet our total accrual goal of 50 response-evaluable patients in 12-16 months or less.

### **11.3 Analysis of secondary endpoints:**

- To assess toxicity of sorafenib (BAY 43-9006) in patients with metastatic medullary thyroid carcinoma.
- Measure serum tumor markers calcitonin and carcinoma embryonic antigen (CEA) pre-, during-, and post-treatment to correlate with disease response.
- Correlate nuclear medicine functional imaging [F-18 fluorodeoxyglucose positron emission tomography (PET) scan] data obtained at pre-, during- and post-treatment with tumor response.
- Correlate dynamic-contrast enhanced magnetic resonance imaging (DCE-MRI) data obtained at pre-, during- and post-treatment with changes in tumor permeability and vascularity with tumor response.
- Perform pharmacogenomic studies on procured PBMCs if clinical responses are observed.
- To correlate between the degree of Ras-MAPK signaling inhibition and vascular endothelial growth factor (VEGF) expression in the tumor and clinical response.
- To correlate between the presence and type of RET gene defects in tumor and clinical response.

With little preliminary data on the biological variability of tumor markers, VEGF expression, ERK phosphorylation, RAS-MAPK signaling pathway inhibition, DCE-MRI parameters, or their assay variation in our laboratories, it is difficult to provide the usual sample size estimates given specified levels of significance and power. Our normal procedure is to use preliminary data of variation coupled with clinically based definitions of reasonable differences to be evaluated to arrive at objective sample size estimates. The 16-patient estimate for estimating a confidence interval for the objective response rate may be insufficient for comparisons of biological correlates.

To address this concern, we will perform an initial analysis of data for secondary endpoints from the first eight patients. This analysis will be done solely to estimate variance and to compute formal sample size estimates based on these findings. While we assume that the 16 patients will provide a sample size sufficient to give general indications of the effect of sorafenib (BAY 43-9006) in cohorts for Arms A and B, our interim assessment will allow us to refine the overall sample size estimate. Depending on biological and experimental variation, we will adjust our definition of a clinically important difference using specified levels of significance and power.

## 11.4 Reporting and Exclusions

**11.4.1 Evaluation of toxicity:** All patients will be evaluable for toxicity from the time of their first treatment with sorafenib (BAY 43-9006).

**11.4.2 Evaluation of response:**

- All patients included in the study must be assessed for response to treatment, even if there are major protocol treatment deviations or if they are ineligible. Each patient will be assigned one of the following categories: 1) complete response, 2) partial response, 3) stable disease, 4) progressive disease, 5) early death from malignant disease, 6) early death from toxicity, 7) early death because of other cause, or 9) unknown (not assessable, insufficient data).
- All of the patients who met the eligibility criteria should be included in the main analysis of the response rate. Patients in response categories 4-9 should be considered as failing to respond to treatment (disease progression). Thus, an incorrect treatment schedule or drug administration does not result in exclusion from the analysis of the response rate. Precise definitions for categories 4-9 will be protocol specific.
- All conclusions should be based on all eligible patients.
- Sub-analyses may then be performed on the basis of a subset of patients, excluding those for whom major protocol deviations have been identified (e.g., early death due to other reasons, early discontinuation of treatment, major protocol violations, etc.). However, these subanalyses may not serve as the basis for drawing conclusions concerning treatment efficacy, and the reasons for excluding patients from the analysis should be clearly reported.
- The 95% confidence intervals should be provided.

## APPENDIX A

### Performance Status Criteria

ECOG Performance Status Scale		Karnofsky Performance Scale	
Grade	Descriptions	Percent	Description
0	Normal activity. Fully active, able to carry on all pre-disease performance without restriction.	100	Normal, no complaints, no evidence of disease.
		90	Able to carry on normal activity; minor signs or symptoms of disease.
1	Symptoms, but ambulatory. Restricted in physically strenuous activity, but ambulatory and able to carry out work of a light or sedentary nature (e.g., light housework, office work).	80	Normal activity with effort; some signs or symptoms of disease.
		70	Cares for self, unable to carry on normal activity or to do active work.
2	In bed <50% of the time. Ambulatory and capable of all self-care, but unable to carry out any work activities. Up and about more than 50% of waking hours.	60	Requires occasional assistance, but is able to care for most of his/her needs.
		50	Requires considerable assistance and frequent medical care.
3	In bed >50% of the time. Capable of only limited self-care, confined to bed or chair more than 50% of waking hours.	40	Disabled, requires special care and assistance.
		30	Severely disabled, hospitalization indicated. Death not imminent.
4	100% bedridden. Completely disabled. Cannot carry on any self-care. Totally confined to bed or chair.	20	Very sick, hospitalization indicated. Death not imminent.
		10	Moribund, fatal processes progressing rapidly.
5	Dead.	0	Dead.

## APPENDIX B

### Sample Shipping Instructions

#### a) Research peripheral blood ([Section 7.4](#))

- All samples must have a label that includes subject no, name of the institution, date/time of collection, and 'NCI 7609'.
- All samples must be shipped on the same day of collection.
- Ship on Monday-Friday only.
- Notify the technician of impending arrival of the sample.
- Ship at room temperature to the following address by overnight mail for AM delivery.

### **Introduction:**

The purpose of this site manual is to document the standard imaging procedure, serve as a handy reference in case of questions and as an information resource.

This document will be subject to revisions, so please make sure that you have the most recent manual.

This document does not supersede any trial document or IRB (Internal Review Board or local Ethics committee) guidelines or requirements.

In case of any **questions**, do not hesitate to contact the protocol chair, the Study Imaging expert and copy the Imaging Trial Lab. All appropriate information is found in the *Contact Section* of this document.

Please inform the Imaging Corelab of any changes in equipment and procedures, and use the *Equipment and Procedure Checklist Section* check list for guidance. If you are unsure about any topic or question, please contact the above resources with details in the *Contact Section* of this document.

Dynamic contrast enhanced MRI (DCE-MRI) will provide data revealing the changes in the vascular perfusion and permeability characteristics of tumors. Successful biologic inhibition will reduce both vascular perfusion and permeability causing a decrease in the peak and rate of contrast enhancement. Dynamic MRI therefore offers a more direct biologic 'in vivo' assessment of therapeutic efficacy.

### **Imaging relevant components of the overall protocol:**

Dynamic contrast enhanced MRI (DCE-MRI) will provide data revealing the changes in the vascular perfusion and permeability characteristics of tumors. DCE-MRI therefore offers a more direct 'in vivo' assessment of efficacy.

Imaging time is estimated at **45-60** minutes per scan.

Standard morphologic MRI sequences (scanning has to cover all tumor areas in at least two planes (such as axial and coronal)) will be used for tumor size determination for all patients undergoing DCE-MRI. These standard sequences (see 1 and 2 below) are performed without contrast; sequences used should be the same at all time points for a given patient. These standard sequences are performed at any time point requiring tumor size measurement. At those time points where DCE-MRI is to be performed, the DCE-MRI protocol is performed after the standard pre-contrast sequences. The standard imaging follows your institutional protocol and should include:

1. T2 weighted (Fast or turbo spin echo) breath-hold
2. T1 weighted Fast Multi-planar Gradient Recalled Echo breath-hold

Both sequences will be performed in the plane suitable to the studied body part. Axial will be the standard plane with better than 2.5 mm in plane resolution and 8 mm slice thickness. Further planes may be implemented as appropriate. The same plane and slice thickness must be used for tumor measurements.

Uni- and bi-dimensional measurements of disease will be recorded of all tumors that can be measured and documented. These measurements and the clinical decision-making accompanying the measurements will be made at the site.

At timepoints where DCE-MRI is being performed, prior to imaging, an IV cannula with a long line is inserted into an arm vein (the ante cubital fossa where possible) for contrast injection.

After completion of the standard sequences, the supervising radiologist will then plan a oblique - coronal slice for the dynamic study which will include the target lesion and major artery such as the aorta or iliac artery. This will remain the studied lesion throughout the trial. T1- and T2-weighted images should be used to select the target lesion and the position for the dynamic image set. For consistency the slice should traverse the mid-line of the tumor. Where possible highly necrotic tumor lesions should **NOT** be selected for the DCE-MRI.

A T1-weighted dynamic contrast enhanced sequence (3D spoiled gradient echo) will then be performed.

Three additional measurement series (5 repetitions each) similar to the DCE sequence will be performed with three different low flip angles for normalization of MRI signal data.

A low molecular weight Gd-chelate MRI contrast agent licensed for i.v. use in humans 0.1 mmol/kg body weight will be injected, preferably by power injector. Injection will commence **after 5th** (fifth) measurement in order to allow a steady state to develop and to provide baseline signal intensities. Power injector rate should be 0.6 ml/sec. Contrast injection is followed by a 20 ml saline flush, also injected at the same speed. Contrast agent and injection technique should be the same at each visit for a given patient.

Because the individual measurements are rapid, breath-hold is not required. As the plane of imaging is in a coronal /oblique orientation, quiet breathing has to be encouraged.

From this dynamic imaging sequence, data will be obtained showing an increase in signal intensity in the various areas over time. The area of maximum enhancement of the tumor will be used for the tumor region of interest (ROI). Regions of interest will also be taken from a major arterial vessel such as the aorta.

The signal intensity versus time data for the tumor, and the major artery (aorta, carotid or iliac artery) will be graphed. From these enhancement curves, several parameters will be calculated including the AUC under the contrast enhancement curve, peak enhancement,  $K_i$  and  $K_{trans}$  (transfer coefficient, a parameter similar to  $K_i$ ) as well as  $A$  [Amplitude] and  $k_{ep}$  [exchange rate constant]. Where necessary for calculation, the low flip angle sequences will be used to normalize data. Data will be presented as % of baseline value of a given parameter.

Studies will be stored in the PACS system, on MR manufacturer-specific storage media as an exact copy for trial purposes and will be forward per FTP to the imaging corelab.

Clinical decision-making will be made on the basis of on-site reading of tumor dimensions from the standard MR images. DCE-MRI is done as laboratory correlative study and will not be used to assess objective response per RECIST. An independent central analysis of combined multi-site DCE-MRI data will be performed, but not used for clinical care.

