#### 9.1.1 Measurable disease

Measurable lesions are defined as those that can be accurately measured in at least one dimension (longest diameter to be recorded) as  $\geq 20$  mm with conventional techniques (CT, MRI, x-ray) or as  $\geq 10$  mm with spiral CT scan or MRI performed with following technique:

MRI images acquired in at least two imaging planes (such as axial and coronal) that give 'in-plane' resolution of at least 2.5 mm.

All tumor measurements must be recorded in millimeters (or decimal fractions of centimeters).

Note: Tumor lesions that are situated in a previously irradiated area will not be considered measurable unless the lesion in irradiated area shows progression.

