### 9.2 Guidelines for Evaluation of Measurable Disease

All measurements should be taken and recorded in metric notation using a ruler or calipers. All baseline evaluations should be performed as closely as possible to the beginning of treatment and never more than 4 weeks before the beginning of the treatment.

Note: Tumor lesions that are situated in a previously irradiated area will not be considered measurable unless the lesion in irradiated area shows progression.

The same method of assessment and the same technique should be used to characterize each identified and reported lesion at baseline and during follow-up. Imaging-based evaluation is preferred to evaluation by clinical examination when both methods have been used to assess the anti-tumor effect of a treatment.

**Clinical lesions.** Clinical lesions will only be considered measurable when they are superficial (e.g., skin nodules and palpable lymph nodes). In the case of skin lesions, documentation by color photography, including a ruler to estimate the size of the lesion, is recommended.

**Chest x-ray.** Lesions on chest x-ray are acceptable as measurable lesions when they are clearly defined and surrounded by aerated lung. However, CT is preferable.

**Conventional CT and MRI.** These techniques should be performed with cuts of 10 mm or less in slice thickness contiguously. Spiral CT should be performed using a 5 mm contiguous reconstruction algorithm. This applies to tumors of the chest, abdomen, and pelvis.

**Ultrasound (US).** When the primary endpoint of the study is objective response evaluation, US should not be used to measure tumor lesions. It is, however, a possible alternative to clinical measurements of superficial palpable lymph nodes, subcutaneous lesions, and thyroid nodules. US might also be useful to confirm the complete disappearance of superficial lesions usually assessed by clinical examination.

**Endoscopy, Laparoscopy.** The utilization of these techniques for objective tumor evaluation has not yet been fully and widely validated. Their uses in this specific context require sophisticated equipment and a high level of expertise that may only be available in some centers. Therefore, the utilization of such techniques for objective tumor response should be restricted to validation purposes in reference centers. However, such techniques may be useful to confirm complete pathological response when biopsies are obtained.

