### **The Imaging Procedure:**

The following information details the imaging procedure. Please note that this does not detail information you will need to enter into the Case Report Form. The imaging procedure need to be adhered to, but was designed to be comparable with your local procedures. The most unique feature of this imaging series is the dynamic imaging sequence used to monitor the contrast agent passage.

Upon registration of the patient for the exam please verify that the patient has signed the informed consent form.

Please assign or get a unique trial patient identifier which will be used for identification purposes in the anonymized image assessment.

Please make sure that the patient understands the imaging procedure and that her or his cooperation is essential for best quality. Please explain that multiple imaging sequences will be acquired and that you will be giving instructions and comments via the intercom.

Prior to imaging an i.v. cannula with a long line is inserted into a vein in the arm (the ante cubital fossa where possible) for contrast injection. In the undesirable event that a different route of access has to be chosen, please document it appropriately.

The imaging procedure consists of the following steps:

- i. Localizer series
- ii. Pre-contrast T2w

- iii. Pre-contrast T1w
- iv. Pre-contrast low flip angle series (same parameters as the dynamic sequence, flip angles set to 4°, 8° and 12°)
- v. Dynamic Series with injection of the contrast agent
- vi. Post-contrast imaging as necessary
- vii. Image archiving, clinical plus trial copy
- viii. Image anonymization and data transfer to the Imaging Core Lab

The overall imaging time is estimated at 45 minutes per procedure. Standard sequence scanning should cover the whole liver including all tumor areas.

For the pre-contrast T1w scan, a T1-weighted Fast Multi-planar Gradient Recalled Echo or balanced-field echo (FIESTA, TRUEFISP) breath-hold sequence will be used.

For the T2 weighted image set, a Fast or Turbo Spin Echo breath-hold sequence will be used. Axial imaging will be the standard plane with 8 mm slice thickness. Further planes may be implemented as appropriate. The same plane and slice thickness must be used for tumor measurements in the follow up procedures.

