**Imaging procedure (Sample of a 1.5T GE system (will be tailored to site specific system):**

1. Localizer
2. Pre-contrast T2- weighted axial images covering the entire neck and upper thorax (according to the standard protocol for thyroid cancer); TR 2450, TE 104.2, Flip 90°, thick: 4 mm, 256x256 .
3. Pre-contrast T1- weighted axial images covering the same volume; TR 400, TE 9.0, Flip 90°, thick: 4 mm, 256x256
4. Identify appropriate target lesion and position the target volume in oblique coronal to have at least one slice through the carotid artery or aorta
5. **Parameter for Dynamic Series:**

Type: GE, saturation recovery FGRET, PSD Filename: ufgret

Repetitions in dynamic series: 100

Averages: 1

Bandwidth: 244 Hz/pixel equals 62.5 kHz

Field of view: 500 mm

Flip: 25 deg.

Slice Thickness: 8 mm Spacing (gap): 2 mm

TE: 3.092 msec TR: 10.287 msec

Matrix: 256 x 256 Voxel size (approx.) 1.8 x 1.8 x 8.0 mm^3

6. Pre-contrast T1w image set (5 repetitions, parameters of the dynamic sequence with the saturation pulse turned off. All other dynamic images with pulse turned on)
7. Dynamic Series with injection of the contrast agent (Contrast injection **after the fifth** measurement. Injected volume: 0.1mmol/kg bw followed by 30 ml saline flush. Injection rate is 2.0 ml/sec for contrast and saline injection.)
8. Post-contrast Imaging as necessary (T1-weighted similar to 3.)
9. Image archiving, clinical plus trial copy on separate media
10. Image anonymization and data transfer to the Imaging Core Lab. Send e-mail that study was performed to [[contact]](mailto:[contact]) and please report any technical issues, dosage and patient weight.
11. In case of questions, please do not hesitate to contact in addition to your local staff: TBA or [name], at the Imaging Core Lab at OSU [[contact]](mailto:[contact]) and cc [[contact]](mailto:[contact])

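### Section 9.1.1 accepts 10 mm lesions on MRI with no slice-thickness condition while Appendix C sets 8 mm slices (4 mm in its sample sheet), exposing patients with one or two small targets to false progression

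*Combined protocol and SAP*

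**What the plan says.** Section 9.1.1 sets two size limits: 20 mm with conventional techniques, and 10 mm with spiral CT or with MRI that meets a stated technique. That technique is "MRI images acquired in at least two imaging planes (such as axial and coronal) that give 'in-plane' resolution of at least 2.5 mm". It names planes and pixels, not slice thickness.

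Section 9.2 caps conventional CT and MRI cuts at 10 mm and adds, for spiral CT only: "Spiral CT should be performed using a 5 mm contiguous reconstruction algorithm".

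Appendix C says that standard MRI sequences "will be used for tumor size determination for all patients undergoing DCE-MRI". Its section on the imaging components of the protocol requires that "scanning has to cover all tumor areas in at least two planes (such as axial and coronal") and then says: "Axial will be the standard plane with better than 2.5 mm in plane resolution and 8 mm slice thickness". The Imaging Procedure section repeats it: "Axial imaging will be the standard plane with 8 mm slice thickness", and adds: "The same plane and slice thickness must be used for tumor measurements in the follow up procedures". The sample site summary sheet at the end of the same appendix gives the axial T2 series as "TR 2450, TE 104.2, Flip 90°, thick: 4 mm, 256x256", and the T1 series is also 4 mm.

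Section 9.3.1 defines PR as a fall of at least 30% in the sum of longest diameters from baseline. PD is a rise of at least 20% from the smallest sum since treatment started. Section 9.4.1 requires a repeat assessment for PR and CR, not for PD. Section 9.3.3 counts best response only up to progression.

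**The concern.** The protocol's CT limits keep the smallest measurable lesion at two slice thicknesses. The MRI limit does not, and a site that follows every section can still size a 10 mm lesion on 8 mm slices. Near that size, the apparent diameter depends on where the slice boundaries fall, and nothing fixes slice position between visits.

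The effect is asymmetric. A spuriously low reading rarely becomes a confirmed PR, because the repeat scan has to agree. The same low reading does become the reference for PD, so a later correct reading can look like progression. That call stands without confirmation and ends the period in which a response can count. A later true response would then be lost to the 2-of-16 and 5-of-25 rules in section 11.1.

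Section 7.3 prefers DCE-MRI in at least 16 patients per arm, out of 16 or 25, so the affected series could size a large part of each arm.

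**Working it through.** **1. The plan's own figure.** For the section 11.1 design (stop at 1 or fewer of 16; positive at 5 or more of 25), exact binomial calculation gives type I error 0.0951 at p = 0.10 and power 0.9030 at p = 0.30. The stated error rates of 0.10 reproduce.

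**2. Lesion-to-slice ratios (9.1.1, 9.2, Appendix C).** Conventional: 20/10 = 2. Spiral CT: 10/5 = 2. MRI series: 10/8 = 1.25. At the sample sheet's 4 mm: 10/4 = 2.5.

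**3. Slice position alone.** Assume a sphere of radius R on contiguous slices of thickness T, with the edge drawn where the lesion fills half the slice. Slice centred on the lesion: d = 2√(R² − T²/16). Slice boundary through the centre: d = 2√(R² − T²/4).

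| True diameter | T | Range read | Largest fall / rise |
|---|---|---|---|
| 10 mm | 8 mm | 6.00–9.17 mm | −34.5% / +52.8% |
| 12 mm | 8 mm | 8.94–11.31 mm | −21.0% / +26.5% |
| 20 mm | 8 mm | 18.33–19.60 mm | −6.4% / +6.9% |
| 10 mm | 5 mm | 8.66–9.68 mm | −10.5% / +11.8% |
| 10 mm | 4 mm | 9.17–9.80 mm | −6.4% / +6.9% |

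At T = 8 mm:
- The +20% line is reachable below a true diameter of 13.2 mm.
- The −30% line is reachable only below 10.5 mm: R² = (16 − 0.49 × 4)/0.51 = 27.5.
- To read 10 mm at all, a sphere must be at least 2√(25 + 4) = 10.8 mm. Slice position alone therefore cannot turn a measurable baseline into a PR.

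**4. False PD over follow-up.** Add an in-plane error uniform within half a pixel at each edge. Draw slice position independently at each scan, require each lesion to read at least 10 mm at baseline, and take three follow-up scans with no true change, read on one plane. Probability of at least one PD against the nadir (400,000 draws per cell before the baseline condition):

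| Targets | 8 mm / 2.5 mm | 8 mm / 1.5 mm | 5 mm / 2.5 mm | 5 mm / 1.5 mm |
|---|---|---|---|---|
| one 12 mm | 35% | 19% | 28% | 5% |
| two 12 mm | 15% | 5% | 8% | 0.2% |
| one 15 mm | 25% | 7% | 16% | 0.4% |
| one 20 mm | 5% | 0.1% | 3% | 0% |

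The 1.5 mm pixel is an illustrative value, not from the documents. For the sole 12 mm lesion at 8 mm/2.5 mm, the first comparison with baseline gives only about 3%. Most of the 35% arises later, against a low nadir.

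**5. False PR and type I error.** In the same model, confirmed false PR for a sole 12 mm lesion is about 0.1%. If a fraction q of non-responders were falsely called PR, p becomes 0.10 + 0.90q. Take the extreme in which every patient has a sole 10 mm lesion sized on MRI:
- Readings rounded to whole 2.5 mm pixels: q = 0.26%, p = 0.1023, type I error 0.1026.
- Half-pixel edge error, all 10 mm lesions: q = 1.0%, p = 0.109, type I error 0.1256.
- Half-pixel edge error, only the 14% of 10 mm lesions that read at least 10 mm at baseline: q = 4.5%, p = 0.1405, type I error 0.263. This would require every patient's only lesion to be 10 mm and over-read at entry.

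**The case against.** Much of the case on the other side stands.

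- Both 9.1.1 and Appendix C require two planes, and a coronal view can show what axial slices blur. The same-plane rule in Appendix C concerns consistency over time. A reader might infer that it confines sizing to the axial plane and cancels the second one; the text does not say so. What stays open is which plane governs, and what slice thickness applies to the other.
- The 2.5 mm figure is a ceiling, not the set pixel size.
- DCE-MRI is optional and is waived where MRI does not suit RECIST (7.3). CT or MRI is the investigator's choice (section 8).
- Target lesions are chosen for size and repeatability and summed over up to 10 (9.1.3), which dilutes the error.
- PD ends treatment only where there is no clinical benefit (4.3), and independent review of responses is strongly recommended (9.5). Neither reopens the best-response window after a false PD.
- The imaging manual does not supersede the protocol. That does not cure the mismatch, because 8 mm breaks no protocol rule: 9.1.1 is silent and 9.2 allows 10 mm.

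The result also depends on the edge rule. With a 30% fill edge instead of 50%, single-comparison false PD for a 10 mm lesion with no baseline condition falls from 21% to 12.5%.

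**Conclusion.** The mismatch is real and Appendix C contradicts itself on slice thickness. The point merits an amendment but does not undermine the design.

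The exposure is false PD in DCE-MRI patients with one or two small targets: about 35% for a sole 12 mm lesion over three scans at 8 mm/2.5 mm, 15% for two such lesions, and 5% for a sole 20 mm lesion. These are upper bounds on the slice-and-pixel effect, for the reasons given under the objection. They assume spherical lesions, a 50% edge rule, independent slice positions and no reader error. The documents give neither lesion sizes nor time to response, so the number of responses lost cannot be computed. Only a response that appears after the false PD is at risk.

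A reader might infer that slice position and pixel size inflate the response rate itself. The documents do not support that as the main risk. A lesion must read 10 mm to be a target, PR must be confirmed, and confirmed false PR is about 0.1% at 12 mm. Even with a sole 10 mm lesion in every patient, type I error moves from 0.095 to about 0.103 with whole-pixel readings (0.126 with continuous edge error).

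**What to change.** In 9.1.1, make the 10 mm MRI limit conditional on contiguous slices of 5 mm or less, matching what 9.2 requires for spiral CT. For thicker MRI slices, require at least 20 mm for a target lesion, or size the lesion by spiral CT. Reconcile the 8 mm in the two Appendix C sections with the 4 mm in the sample site sheet. Apply the change to newly enrolled patients, so that each patient keeps one technique throughout.

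The slice limit removes the slice-position part of the error. It does not remove the pixel part: at the 2.5 mm ceiling, a sole 12 mm lesion still gives 28% at 5 mm slices. The documents offer no basis for a particular finer pixel limit, so none is proposed here.

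The cost is amendment wording and a somewhat longer standard MRI series, or CT sizing for a few patients with only small lesions. Slices of 4 mm are already in the manual's sample sheet.
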